#### XIV. STATISTICAL ANALYSIS AND DATA MANAGEMENT

Data analysis will be performed by the Sponsor's Statistician; the contract lab will summarize Oral Soft and Hard Tissue findings, Sensory Responses and Adverse Events by product and time point.

#### **Demographic Data and Baseline Comparability**

The table of demographic information will include the count and percent for each gender and for each ethnic group, as well as descriptive statistics (mean, median, standard deviation, minimum and maximum) for age. Comparisons between the treatment groups with respect to gender and ethnic group will be performed using chi-squared tests. The comparison between the treatment groups with respect to age will be performed using a t-test.

#### Sample Size

The planned sample size for this study is to complete with at least 100 evaluable subjects per treatment group (300 total subjects). Approximately 320 subjects will be enrolled, to assure that at least 100 evaluable subjects per group complete the study. Based on a 3-month pilot clinical study, in which the coefficient of variation for the plaque index (PI) was 18.1%, the coefficient of variation for the gingival index (MGI) was 7.2%, and the coefficient of variation for the bleeding index (GBI) was 61.3%, 100 subjects per group will give a power of over 95% for detecting a 20% difference between groups.

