#### V. SUBJECT POPULATION

#### **Number of Subjects**

Approximately 320 subjects will be enrolled to ensure that 100 subjects per group (300 total) will be expected to complete the 6-month study. Subjects will be selected from the study site's database of subjects located in the Mississauga, Ontario area. Volunteers must read and sign the Informed Consent Form after the nature of the study has been fully explained.

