#### VI. STUDY DESIGN

This parallel group, double-blind, randomized, single center, IRB/IEC-approved study will enroll approximately 320 subjects to ensure that approximately 100 subjects per group (300 subjects total) will complete the 6-month study. The Study Examiner will screen for subjects that meet the enrollment criteria. Subject group stratification will be based on smoking and tobacco use. Subjects will be randomly assigned to one of three dentifrice treatment groups. Oral soft and hard tissue examinations, gingivitis, bleeding and plaque assessments will be done at baseline and after 6 weeks and 3- and 6-months. Following an initial supervised tooth brushing, subjects will brush unsupervised with their assigned toothpaste at home for the 6-month treatment phase of the study, 2 times daily for 1 minute per brushing. Subjects will be provided with a timer and will maintain a daily diary of their brushing and record any oral effects they experience. Compliance will be assessed by subject diary and weight-loss of returned test products at each visit. The examiner will be blinded to the product codes/identification and product assignments.

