#### VII. SUBJECT ASSIGNMENT TO TREATMENT GROUPS

At the baseline visit, following the clinical assessments, the study population will be evenly distributed into three treatment groups of approximately equal size and equivalence. Qualified subjects will be randomly assigned to the three treatment groups based on a randomization scheme developed using the baseline plaque and gingival assessment scores and age for stratification. The study staff responsible for random assignments will be blinded to the product treatments. Allowance will be made for members of the same household co-habiting at one address to receive the same products to prevent inadvertent switch-over.

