#### XIII. SUBJECT COMPLETION AND WITHDRAWAL

#### **Subject Completion**

Only subjects who complete all procedures and comply with all areas of the protocol will be deemed to have completed the study. Subjects will be compensated for their time and travel and for successfully completing all provisions and procedures of the study. If a subject voluntarily withdraws from the study, or if withdrawn by the Investigator for any reason, he/she will be compensated as agreed upon with All Sum Research. Subject compensation will be documented in the Informed Consent and will be approved by the IRB/IEC.

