#### **Subject Withdrawal**

Subjects are free to withdraw at any time during the clinical trial. Subjects may also be withdrawn from the study at any time at the discretion of the Investigator and/or the Sponsor. All subject withdrawals will be documented in the study file. Where possible, the reason for the withdrawal will be documented. Any withdrawals as the result of an adverse event will be followed-up at the discretion of the Study Investigator. Withdrawn subjects will not be replaced.

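### Enrolling about 320 does not assure 100 evaluable subjects in every group, and the blanket power claim tied to that size fails for GBI even at a full 100

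*Combined protocol and SAP*

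**What the plan says.** The combined protocol and SAP gives the size in three places, with different strength.

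- Sample Size (section XIV) sets a minimum: "The planned sample size for this study is to complete with at least 100 evaluable subjects per treatment group (300 total subjects". It then says: "Approximately 320 subjects will be enrolled, to assure that at least 100 evaluable subjects per group complete the study". It attaches power of over 95% for a 20% difference to 100 per group, for three indices with pilot CVs of 18.1% (PI), 7.2% (MGI) and 61.3% (GBI).
- Number of Subjects (section V) gives an expectation: "Approximately 320 subjects will be enrolled to ensure that 100 subjects per group (300 total) will be expected to complete the 6-month study".
- Study Design (section VI) is looser again: "approximately 100 subjects per group (300 subjects total) will complete the 6-month study".

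Three rules bear on how many subjects remain. Subject Withdrawal says: "Withdrawn subjects will not be replaced". Efficacy Analysis bases the primary analysis on subjects who complete every visit. Section VII plans groups of about equal size but adds: "Allowance will be made for members of the same household co-habiting at one address to receive the same products". No section states an expected loss rate or a probability of reaching the target.

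**The concern.** A minimum that must hold in each of three groups is harder to meet than an average of 100. Enrolling 320 to finish with 300 leaves 20 losses to share: 7, 7 and 6 if the groups are 107, 107 and 106. Nothing in the plan absorbs chance variation around that. Because the primary analysis uses completers and there is no replacement, each loss reduces the primary sample.

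The power statement rests on the same figure of 100. What is at stake is whether a reader can rely on the stated size and on one power figure covering three indices with very different variability. Bleeding is part of the primary objective, so GBI matters as much as MGI here.

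**Working it through.** **Inputs.** From Sample Size: 320 enrolled; at least 100 per group (300 in total); CVs of 18.1%, 7.2% and 61.3%; a 20% difference. From Efficacy Analysis: two-sided alpha 0.05 and Tukey-adjusted pairwise comparisons. From section VII: three groups of about equal size, taken as 107/107/106. Loss rate: not stated, so a range is used.

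**1. The plan's enrolment figure.** (320 − 300)/320 = 6.25%, and 300/(1 − 0.0625) = 320. This is circular, because the rate comes from the two totals. It shows only that 320 gives 300 on average at 6.25% loss.

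**2. Chance that every group reaches 100.** With independent losses at rate d, the chance is P(X₁₀₇ ≥ 100)² × P(X₁₀₆ ≥ 100), where Xₙ is binomial(n, 1 − d).

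| Loss d | Group of 107 | Group of 106 | All three |
|---|---|---|---|
| 3% | 0.985 | 0.959 | 93% |
| 5% | 0.833 | 0.720 | 50% |
| 6.25% | 0.647 | 0.504 | 21% |
| 8% | 0.370 | 0.247 | 3% |
| 10% | 0.150 | 0.085 | 0.2% |

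Example at 6.25%: 0.6467² × 0.5038 = 0.211. A 90% chance needs loss of about 3.2% or less. Other models at 6.25% give 27% (107 in every group), 4% (exactly 20 losses falling at random) and 2% (unrestricted randomisation of 320). The even split is a favourable assumption, since the household rule could unbalance the groups.

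**3. How large a shortfall is likely.** At 6.25% loss the smallest group has a median of 98 completers, and all three groups reach 95 with probability 0.984² × 0.967 = 0.94.

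**4. Power at 100 per group.** Read the CV as SD/mean, so the standardised difference is 20/CV and the noncentrality is (20/CV) × √(n/2). The critical value is 1.972 unadjusted (198 df). With Tukey for three groups (297 df) it is 3.331/√2 = 2.356.

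- PI: 20/18.1 = 1.105; noncentrality 7.81; power above 99.9% either way.
- MGI: 20/7.2 = 2.778; noncentrality 19.6; power above 99.9% either way.
- GBI: 20/61.3 = 0.326; noncentrality 2.307. Unadjusted power is about Φ(2.307 − 1.972) = 63%; with Tukey, about Φ(2.307 − 2.356) = 48%. Noncentral-t values are 63.2% and 48.2%.

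The claim of over 95% therefore reproduces for PI and MGI but not for GBI. Unadjusted 95% power for GBI would need about 2 × (1.960 + 1.645)²/0.326² ≈ 245 per group.

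**5. What attrition adds.** From 100 to 95 per group, GBI power falls from 63.2% to 60.9% unadjusted and from 48.2% to 45.8% with Tukey. PI and MGI stay above 99.9%.

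**6. Power at the expected sizes.** 320 × 0.95/3 ≈ 101; 320 × 0.90/3 = 96; 320 × 0.85/3 ≈ 91. GBI power with Tukey is about 49%, 46% and 44%.

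**7. Baseline covariate.** If the pilot CV describes unadjusted scores, a baseline correlation ρ multiplies the variance by 1 − ρ². For 95% power with Tukey at 100 per group the noncentrality must be about 2.356 + 1.645 = 4.00. So 1 − ρ² = (2.307/4.00)² ≈ 0.33, and ρ ≈ 0.82. The documents give no correlation.

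**The case against.** The strongest reply is that this is a matter of wording. Number of Subjects and Study Design already say what the plan can support, enrolment is itself approximate, and subject numbers in Subject Identification run to 330. Any enrolment inflated by the usual n/(1 − d) rule has a modest chance of meeting a minimum in all three arms: for example, about 30% with 112 per arm at 10% loss. The likely shortfall is a few subjects and its effect on power is slight. All of this stands, and it makes the attrition part minor. It does not rescue the Sample Size sentence, which is the one that carries the power claim and keeps its target at about 320.

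Three stronger readings are tempting but unsupported.

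- A reader might take 21% as the plan's own chance of success. The plan states no loss rate; at 3% loss the chance is 93%.
- A reader might infer that heavy losses are built in, because "Only subjects who complete all procedures and comply with all areas of the protocol will be deemed to have completed the study". But the primary analysis is defined by completing visits, and Product Use Compliance says subjects who appear out of compliance by product weight are re-instructed. Subject Discontinuation does list non-adherence, but no figure in the documents points to 8%, 10% or 15%.
- A reader might blame dropout for weak GBI power. The GBI shortfall is there with no dropout at all.

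On GBI itself, the fair objection is that the planned ANCOVA could raise power above the figures here. That is true, but without a stated correlation the gain cannot be credited.

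**Conclusion.** The point holds in two parts of unequal weight.

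The minor part: 320 gives about 100 per group on average at about 6% loss and does not assure it in every group unless loss is about 3% or less. This rests on independent losses and a near-even split; every other model tried at 6.25% also falls far short of assurance (2% to 27%).

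The larger part: one figure of over 95% power cannot cover all three indices. It is right for PI and MGI. For GBI at 100 per group it is about 63% unadjusted and 48% under the planned Tukey comparisons. This rests on reading the CV as SD/mean and on no credit for baseline adjustment. Neither part shows that the trial must enrol more, and the documents do not support saying that attrition undermines the PI or MGI comparisons.

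**What to change.** Change the Sample Size text only.

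1. Align it with Number of Subjects and Study Design, for example: *about 320 will be enrolled; about 100 per group are expected to complete if loss is about 6%.* Label the loss rate as an assumption.
2. Replace the single power statement with power for each index under the Tukey comparisons at the sizes expected for 5%, 10% and 15% loss:

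| Per group | PI | MGI | GBI |
|---|---|---|---|
| about 101 | >99.9% | >99.9% | about 49% |
| 96 | >99.9% | >99.9% | about 46% |
| about 91 | >99.9% | >99.9% | about 44% |

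3. If a gain from the baseline covariate is claimed for GBI, state the correlation assumed and its source.

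Enrolment, design and analysis do not change. The cost is that the stated size reads less firmly and the stated GBI power becomes clearly less favourable.

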#### STUDY OBJECTIVES

The objectives of this 6-month clinical research study are:

- 1) Primary objective is to evaluate the safety and efficacy of two baking soda dentifrices, containing 20% and 35% baking soda, (test products) compared to that of a non-baking soda dentifrice (negative control) in reducing gingival inflammation and bleeding.
- 2) Secondary objective is to evaluate the efficacy of two baking soda dentifrices compared to that of a non-baking soda dentifrice in reducing plaque.

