#### **Efficacy Analysis**

The primary analysis will be conducted on the population of subjects who complete all study visits. A secondary analysis will be conducted on the intent to treat population; that is, at each time point, all subjects who completed both the baseline evaluation and that evaluation will be included in the analysis. Additional subsets of the subject

population may be analyzed for informational purposes only. Other than the subject inclusion criterion, all analyses will be conducted identically as follows:

For each examination and each index, subjectwise mean Index scores will be obtained by calculating the average of the index scores evaluated at all individual measurement sites within the mouth. In addition to these 'whole-mouth' scores, subjectwise scores will also be obtained by calculating the average index scores over selected subsets of sites within the mouth. These subsets will include: Proximal sites; Marginal sites (MGI and GBI only); Gingival sites (PI only); Facial sites; Lingual sites; Posterior sites; Anterior Facial sites; and Anterior Lingual sites.

All statistical analyses will be based on the subjectwise Index scores. Separate analyses will be performed based on the subjectwise whole-mouth scores, as well as the subjectwise scores obtained from each of the selected subsets of the mouth.

The primary endpoints employed for the treatment comparisons in this study will be the month 6 Index scores. Additional analyses will be conducted on the Index scores collected at other time points. The comparison of the study treatments will employ an analysis of covariance (ANCOVA) model, with the associated baseline Index score included as a covariable. The ANCOVA model will include the factors: subject, treatment, and baseline Index score. Post-ANCOVA pairwise treatment comparisons of the adjusted means will be performed using t-tests utilizing Tukey's adjustment for multiple comparisons. Within-treatment comparisons of the mean baseline Index scores to the mean month 6 (or other post-baseline time point) Index scores will be performed using paired t-tests.

The comparison of the study treatments at baseline for each index will be performed using the same model described above, without the inclusion of the covariable.

All statistical tests of hypotheses will be two-sided, and employ a level of significance of  $\alpha = 0.05$ .

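### The stated power of over 95% for a 20% difference holds for plaque and gingival inflammation but not for bleeding, where the plan's own CV gives 63% (48% with Tukey) before any covariate gain

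*Combined protocol and SAP*

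**What the plan says.** The Sample Size section gives three CVs: 18.1% for PI, 7.2% for MGI and, for bleeding, "the coefficient of variation for the bleeding index (GBI) was 61.3"%. Their source is given as "Based on a 3-month pilot clinical study". One conclusion follows, with no limit by index: "100 subjects per group will give a power of over 95% for detecting a 20% difference between groups". The section names no test, multiplicity adjustment or correlation. It does not say whether the CVs are raw or residual, or to which mean and scale the CV and the 20% refer.

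The Study Objectives section makes bleeding part of the primary objective: the test dentifrices are "compared to that of a non-baking soda dentifrice (negative control) in reducing gingival inflammation and bleeding". Under Efficacy Analysis, "The primary endpoints employed for the treatment comparisons in this study will be the month 6 Index scores". The model there is an ANCOVA "with the associated baseline Index score included as a covariable". "Post-ANCOVA pairwise treatment comparisons of the adjusted means will be performed using t-tests" with Tukey's adjustment, and tests are two-sided at 0.05.

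**The concern.** The GBI CV is more than three times the PI CV (61.3/18.1 = 3.4) and about 8.5 times the MGI CV (61.3/7.2), yet one power figure covers all three. A 20% difference is about 1.1 SD for PI and 2.8 SD for MGI, but only about a third of an SD for GBI.

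As written, the plan says that the chance of missing a true 20% difference in bleeding is under 5%. If the CV is taken at face value, that chance is several times larger. A non-significant bleeding result could then be misread as strong evidence against a 20% effect. The documents do not say that 20% is the bleeding effect the sponsor expects, so the point concerns the stated power and not the likely result of the trial.

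**Working it through.** **Inputs.** From Sample Size: 100 evaluable subjects per group in three groups, the three CVs, and the 20% difference. From Efficacy Analysis: two-sided 0.05, baseline covariate, Tukey-adjusted pairwise tests. Not given in the documents, and therefore varied: the meaning of the CV and the baseline-to-month-6 correlation r.

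**Method.** Pairwise power from the noncentral t distribution:

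- Noncentrality = d × √(100/2) / √(1 − r²), where d is the standardised difference.
- Degrees of freedom = 300 − 3 − 1 = 296.
- Critical values: 1.968 unadjusted; 2.356 with Tukey, which is q(0.95; 3, 296)/√2.

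**The plan's figure, by index (common SD, r = 0).**

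| Index | d = 0.20/CV | Noncentrality | Power, unadjusted | Power, Tukey |
|---|---|---|---|---|
| PI | 0.20/0.181 = 1.10 | 7.81 | >99.9% | >99.9% |
| MGI | 0.20/0.072 = 2.78 | 19.64 | >99.9% | >99.9% |
| GBI | 0.20/0.613 = 0.326 | 2.31 | 63% | 48% |

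The figure of over 95% is reproduced for PI and MGI but not for GBI. On this reading, GBI would need a CV of about 39% (35% with Tukey) to reach 95%.

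**Other readings of the GBI CV.** Each takes the CV and the 20% from month 6 group means, with the test group 20% lower. Pairs are unadjusted / Tukey.

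| Reading | d | Power at r = 0 | Difference detectable with 95% power, r = 0 | r needed for 95% power (raw CV) |
|---|---|---|---|---|
| Common SD, reference mean | 0.20/0.613 = 0.326 | 63% / 48% | 31% / 35% | 0.77 / 0.82 |
| SD proportional to each mean | 0.20/(0.613 × √0.82) = 0.360 | 72% / 58% | 27% / 30% | 0.71 / 0.77 |
| Log-normal scores | −ln(0.8)/0.565 = 0.395 | 80% / 67% | 25% / 27% | 0.64 / 0.72 |
| SD from the lower mean | 0.20/(0.613 × 0.8) = 0.408 | 82% / 70% | 24% / 26% | 0.60 / 0.69 |

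Here 0.82 = (1 + 0.8²)/2, and 0.565 = √ln(1 + 0.613²).

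**Covariate gain if 61.3% is a raw CV (range over the four readings).**

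| Assumed r | Unadjusted | Tukey |
|---|---|---|
| 0.3 | 67–85% | 53–75% |
| 0.5 | 76–91% | 62–83% |
| 0.7 | 90–98% | 81–95% |

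If 61.3% is already a residual CV, no covariate gain remains and the r = 0 figures apply. A simulated three-arm ANCOVA (4,000 runs per setting; three of the four readings; r = 0, 0.5 and 0.7) agreed with these results within 1.5 percentage points.

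**Further variants for GBI at r = 0, without Tukey.** One-sided test, 74.6%. All 320 enrolled subjects (106.67 per group), 66.4%. Both test arms pooled against control, 75.9%. One-sided with log-normal scores, 87.5%. None reaches 95%.

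**The case against.** The strongest objection is that nothing proves the claim false. The analysis is an ANCOVA on baseline, and with a raw CV a high enough correlation makes over 95% correct for GBI. The documents do not exclude such a value. This stands as far as it goes: the finding is that the stated inputs do not deliver the figure, not that no inputs could. The plan gives no correlation, however, and one from a 3-month pilot would not itself be a month 6 figure.

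A second route is the reference mean. If the 20% refers to a larger mean than the one behind the CV, 95% is reached without a covariate (common SD) once that mean is at least 1.57 times as large, or 1.74 times with Tukey. The documents give no GBI means, so this can be neither confirmed nor excluded, and a smaller reference mean would lower power. The four readings are therefore not an absolute ceiling.

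Third, 63% / 48% is the least favourable of the four readings. That is fair, and the range at r = 0 is 63–82% unadjusted and 48–70% with Tukey. Every value in it is below 95%.

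Finally, the Introduction reports p<0.001 for bleeding in the 12-week pilot. This bears on the practical risk, but without an effect size or sample size it does not establish 95% power for a 20% difference.

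**Conclusion.** The concern holds. The power statement is correct for PI and MGI and is not supported for GBI. Before covariate gain, the chance of missing a true 20% GBI difference is 37% unadjusted (100 − 63) and 52% with Tukey (100 − 48) for a common SD. On the most favourable of the four readings it is 18% and 30%. The plan implies under 5%.

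These figures assume 100 evaluable subjects per group and a CV and 20% difference that refer to month 6 group means. They apply if the CV is residual, or if it is raw and the covariate adds nothing. Because bleeding belongs to the primary objective and the month 6 scores are the primary endpoints, the statement needs to be corrected and not merely annotated.

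**What to change.** Restate the Sample Size paragraph by index, under the planned Tukey-adjusted ANCOVA. Keep over 95% for a 20% difference in PI and MGI. For GBI, state:

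1. whether 61.3% is a raw or a residual CV;
2. the reference mean and scale of the CV and of the 20% difference;
3. if the CV is raw, the assumed baseline-to-month-6 correlation and its source, noting that the pilot lasted 3 months.

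Then give the resulting power. If the CV is residual, or no correlation can be documented, give the power without covariate gain for the reading established in item 2. That is about 48% with Tukey (63% unadjusted) for a common SD relative to the reference mean, rising to about 70% (82%) on the most favourable of the four readings. Also state the difference detectable with 95% power: about 35% with Tukey (31% unadjusted) for the common SD.

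The cost is one reworded paragraph and a look-up in the pilot data. The stated GBI power will be less favourable unless a sufficient correlation is documented. The correction itself requires no change in enrolment; whether the corrected GBI power is acceptable is for the sponsor to decide.
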